6.1.2. Treatment Period

During the 1.5-year study, each patient will receive up to 20 SC doses of ISIS 766720 with a planned monthly interval between each dose except for a booster dose at Day 15 (WK 3). All patients will have bi-weekly visits beginning at Day 1 (WK 1) through Day 113 (WK 17). After that visits occur monthly through Day 505 (WK 73) with an additional visit on Day 183 (WK 27) for primary endpoint assessments. Of the 24 required study visits, 14 selected study visits may be performed outside of the clinic by a Sponsor selected Home Health Care professional (See [Appendix A](#)). Home health visits are optional and would be arranged by study center staff if requested by the patient. In consultation with the Sponsor, a Home Health Care visit may be conducted for a study visit day that was intended to be an in-clinic visit. It is preferable that the entire visit is conducted, however the following assessments may be omitted: ECG, body weight, physical exam, ring size, and OGTT. If a visit cannot be performed in the clinic or by Home Health, patient contact (e.g., phone, text, email or video) is required by site personnel to assess any adverse events or changes in concomitant medications. Any assessments not completed at the Home Health Care visit should be attempted at the next clinic visit.

Safety, efficacy, PK and exploratory assessments will be performed per [Appendix A](#), [Appendix B](#), and [Appendix C](#) throughout the Treatment Period on ISIS 766720 administration days. At each visit, patients should arrive fasting at least 8 hours for safety and clinical laboratory evaluations; vital signs, blood pressure (BP) assessments, AEs and concomitant medication usage will be assessed during each visit.

A 2-hour OGTT and GH response procedure will be conducted pre-dose on Day 1 and pre-dose on Day 183 (WK 27) and Day 505 (WK 73). The pre-dose-Day 1 OGTT and GH response procedure may be conducted between Day -41 and pre-dose Day 1. To decrease the study burden on potential patients, it is suggested that this procedure is done after the patient has completed and qualified based on all other screening procedures. The OGTT and GH Response procedure can be conducted in the clinic or as arranged by a Home Health Care professional. The patient must fast 10-hours prior to OGTT and GH Response assessment.

Quality of life assessments and general health assessments including ASTS-M, AcroQOL, EQ5-D, and SF-36 questionnaires will be assessed along with ring size assessment periodically throughout the study. See Section [6.2.3](#) for a description of the study procedures. Study required procedures at study visits are listed in the Schedule of Procedures in [Appendix A](#), [Appendix B](#), and [Appendix C](#). Patient will be requested to complete AcroQoL, ASTS-M, EQ5-D, and SF-36 and ring size assessments prior to all other procedures and dosing (see Section [6.2](#)).

All blood samples should be drawn prior to ISIS 766720 administration (exceptions are the post-dose samples for PK sampling at Day 1 and Day 113).

An MRI (3×) and Echocardiogram (2×) will be done. See [Appendix A](#) for timing of procedure.

During each visit, the study staff should attempt to complete all the study procedures prior to ISIS 766720 administration as outlined in the [Appendix A](#), however, if a procedure is conducted after ISIS 766720 administration it will be considered a deviation that does not impact the evaluation of efficacy.

All safety data including AEs and concomitant medications will be reviewed by the Sponsor's Medical Monitor or Designee on an ongoing basis throughout the trial. Early termination patients from the Treatment Period will be requested to enter the 14-week Post-Treatment Period. The first visit to complete is an "early termination from treatment" visit entitled ETTX. The ETTX visit should be completed as soon as possible after the decision is made, preferably 4 weeks after the last dose. The remainder of the Post-Treatment visits should then follow the schedule which are in intervals relative to the patients last dose ([Appendix A](#)). All patients receiving at least 1 dose of study medication are required to enter the Post-Treatment Period for continuing safety evaluations. Please contact your CRA at the time of early termination to review the schedule.

6.1.3. Post-Treatment Period

After completing the 73 weeks of the Treatment Period, including patients who discontinue early from the Treatment Period, patients will return for Post-Treatment follow-up evaluations ([Appendix A](#)). All patients will be followed for 14 weeks, the last visit is Post-Treatment Week 15 (PTWk15) occurring 99 days after the last dose. Note: the visits are scheduled in intervals relative to the patient's last dose, for example Post-Treatment Week 5 (PTWk5) is 28 days after the last dose.

Safety and clinical laboratory evaluations as well as PD markers, including those for PK/PD analysis, will be performed as indicated in the [Appendix A](#), [Appendix B](#), and [Appendix C](#). Safety and efficacy data, including any AEs and concomitant medications will be recorded and reviewed by the Sponsor's Medical Monitor or Designee.

The AcroQoL, ASTS-M, EQ5-D, and SF-36 and ring size assessment will be conducted periodically in the Post-Treatment Period.

Early termination patients from the Post-Treatment Period (ETPT) will be required to complete the ETPT Study procedures ([Appendix A](#)).

6.2. Study/Laboratory Assessments

6.2.1. Clinical Laboratory Assessments

Laboratory analyte samples will be collected throughout the study. A list of these analytes is contained in [Appendix B](#). Blood chemistry should be taken after fasting for at least 8 hours (at least 10 hours for OGTT). During this time the patient should ensure that they consume sufficient water in order to not become dehydrated.

If the platelet value, serum creatinine or liver enzyme tests are uninterpretable (e.g., due to clumping, hemolysis or quantity not sufficient) or missing, a repeat blood specimen should be re-drawn as soon as possible (ideally within 7 days) either in clinic or by home health or local laboratory. The next dose of ISIS 766720 may not be administered until a result not meeting a stopping rule is available. See Section [8.5](#) for more guidance. Platelet results must meet the timeframe requirements in Section [8.5.2](#).

At any time, the Sponsor Medical Monitor or designee may request both a local and central laboratory collection in parallel to assess patient safety.

6.2.2. Oral Glucose Tolerance Test and Growth Hormone Response during OGTT

Patients will undergo OGTT and GH response procedures during the study per [Appendix A](#). For each OGTT procedure, patients should be fasting for 10 hours before the test (only water is permitted). It is preferable to collect blood samples for OGTT through indwelling catheter, but it is not mandatory. (See [Appendix A](#) and [Table 1](#)). After an indwelling catheter (if used) is inserted at T-5 minutes, a 5-minute period is allowed to remove any effects linked to the stress induced by venipuncture. Blood sampling will begin before the glucose solution is consumed at Time 0. The glucose anhydrous solution (75 grams in a 300-mL solution) will be consumed within a 5-minute period, after which blood samples will be drawn during the test every 30 minutes from the start time of glucose ingestion during the 2 hours of the OGTT as outlined in [Table 1](#). Patients may drink water during the OGTT but must refrain from eating or drinking any other fluids except water and must refrain from smoking until the fasting period is completed (after the 120-minute blood draw). During the Treatment Period, the OGTT should be completed before ISIS 766720 is administered.

Table 1: Sampling Schedule: Day of Oral Glucose Tolerance Test and GH Response During OGTT

Intervention	Time (Minutes)	OGTT and GH Response Sampling
	-5	Catheter Insertion (if used)
T ₀ = 75 grams Glucose Ingestion	0 Prior to Glucose ingestion	Glucose, Insulin, C-peptide, Growth Hormone
	30	Glucose, Insulin, C-peptide, Growth Hormone
	60	Glucose, Insulin, C-peptide, Growth Hormone
	90	Glucose, Insulin, C-peptide, Growth Hormone
	120 [#]	Glucose, Insulin, C-peptide, Growth Hormone

[#] After the 120-min blood draw, the fasting period is completed

6.2.3. Assessments for Acromegaly

There are up to 5 procedures that will be conducted that assess signs, symptoms and QoL for an acromegaly patient. For purposes of this clinical trial and consistency across visits, it is requested that these assessments for acromegaly be:

1. Conducted at the beginning of the study visit (prior to other study procedures and drug administration)
2. Conducted sequentially in this order: 1) AcroQoL; 2) ASTS-M; 3) EQ-5D; 4) SF-36; 5) Ring Size Assessment. All QoL and health assessment questionnaires will be a paper assessment filled out by patients and the results are entered into eCRF by site staff
3. It may take approximately 40 minutes to complete all 5 assessments

Prior to filling out the QoL and health assessment questionnaires, the patient should sit quietly in a room without distraction, and be reminded of the following; i) the purpose of the questionnaires, ii) to complete the questionnaire honestly, and iii) they should be aware that there are no wrong answers, iv) it is important to answer all questions.

Note: the order of completion of assessments relative to ISIS 766720 administration is a recommended best practice but not a requirement, and therefore will not constitute a deviation if not strictly followed.

6.2.3.1. Acromegaly Quality of Life Questionnaire

To assess the health-related QoL affected by acromegaly, patients will complete the AcroQoL questionnaire during the Treatment and Post-Treatment Periods (per [Appendix A](#)). AcroQoL is a 22-question survey to quantify the self-perceived impact of acromegaly in patients' life. It contains 2 scales that evaluate physical (8 questions) and psychological aspects related to the appearance and personal relations (7 items each) ([Webb et al. 2002](#)). This questionnaire will take about 10 minutes to be completed.

6.2.3.2. Acromegaly Symptoms and Treatment Score Questionnaire-Monotherapy

Patients will be asked to complete the ASTS-M to monitor symptoms relating to acromegaly and its treatments. Each question is answered on a scale of 0 to 4 from no symptom to very severe. The questions address acromegaly-specific symptoms (e.g., headache, perspiration, paresthesia) and treatments (burden of ISIS 766720). This questionnaire will take about 5 minutes to complete.

6.2.3.3. EQ-5D

Patients will be asked to complete the EQ5D which is a standardized instrument for measuring health outcome. It measures 5 health dimensions: mobility, self-care, usual activities, pain/discomfort and anxiety depression. It is used as a quantitative measure of health outcome that reflects the patient's own judgement. Each dimension has 5 levels: no problems, slight problems, moderate problems, severe problems and extreme problems. The patient is asked to indicate his/her health state by ticking the box next to the most appropriate statement in each of the 5 dimensions. This questionnaire will take about 10 minutes to complete.

6.2.3.4. 36-Item Short Form Survey

Patients will be asked to complete the SF-36 which is a set of generic, coherent, and easily administered QoL measures. It measures 8 health concepts: physical functioning, bodily pain, role limitations due to physical health problems, role limitations due to personal or emotional problems, emotional well-being, social functioning, energy/fatigue, and general health perceptions. It also includes a single item that provides an indication of perceived change in health. Each section has different instructions on how to answer the questions. This questionnaire will take about 10 minutes to be completed.

6.2.3.5. Ring Size Assessment

Finger size is an objective measure of soft tissue swelling and overgrowth and can be used to monitor the response to treatment. Measurement should be taken prior to any intravenous cannulation. Ring size is assessed using the study provided ring sizer widget and the 4th finger of the non-dominant hand. The ring size to record is the one with the tightest fit. If the finger is too large to be measured by the ring sizer then use the 5th finger (and make a note of this). The same finger will be used throughout the trial ([Barts Endocrine 2009](#)). The ring size assessment should be completed by the same staff member at each visit if possible.

6.2.4. MRI

MRI of the sellar region will be conducted for all patients for whom MRI is not contraindicated, e.g., patients having metal implants. If the MRI is contraindicated, then a CT scan may be performed. See [Appendix A](#) for timing of procedure.

6.2.5. Echocardiography

Echocardiography for assessment of left and right ventricular function be conducted at times indicated in [Appendix A](#). For the purpose of assessment of treatment-emergent changes, all echocardiograms will be evaluated by an independent central reader.

6.3. Restriction on the Lifestyle of Patients

6.3.1. Contraception Requirements

All male patients and WOCBP must refrain from sperm/egg donation and practice highly effective contraception from the time of signing the ICF until 14 weeks after their last dose of study treatment.

Male patients engaged in sexual relations with a female of child-bearing potential must use highly effective contraception from the time of signing the informed consent until 14 weeks after the patient's last dose of study treatment. If the patient's non-pregnant female partner is using a highly effective contraception method throughout the duration of the study, the requirement for contraception for the male patient is considered fulfilled.

For the purposes of this study, WOCBP are defined as any female who has experienced menarche, and who does not meet 1 of the following conditions:

- Postmenopausal: 12 months of spontaneous amenorrhea in females > 55 years of age or, in females ≤ 55 years, 12 months of spontaneous amenorrhea without an alternative medical cause and FSH levels in the postmenopausal range for the laboratory involved
- 6 weeks after surgical bilateral oophorectomy with or without hysterectomy
- Post hysterectomy

For the purposes of the study, highly effective contraception is defined as follows:

For male patients:

- a vasectomy with negative semen analysis at Follow-up
- sexual abstinence[†]
- Male patients with partners that are pregnant must use condoms to ensure that the fetus is not exposed to the ISIS 766720

For female patients of childbearing potential:

- surgical sterilization (e.g., bilateral tubal occlusion), hormonal contraception associated with inhibition of ovulation (combined [estrogen and progestogen containing] or progestogen-only), intrauterine device (IUD), intrauterine hormone-release system (IUS), a vasectomized partner or sexual abstinence[†]

[†] **Note:** Abstinence is only acceptable as true abstinence, refraining from heterosexual intercourse throughout the duration of study participation. Periodic abstinence (e.g., calendar, ovulation, symptothermal, post-ovulation methods), declaration of abstinence for the duration of a trial and withdrawal are not acceptable methods of contraception.

Note: A female condom and a male condom should not be used together as friction between the 2 can result in either or both products failing.

[figure not shown]
6.3.2. Other Requirements

Patients must refrain from strenuous exercise/activity (for example heavy lifting, weight training, intense aerobics classes etc.) for at least 24 hours prior to each study visit and also be willing to refrain from alcohol or tobacco use for 8 hours prior to study visits and/or laboratory sampling.

All patients will be required to fast for at least 8 hours before laboratory sampling and for at least 10 hours before OGTT and GH response assessments.

7. STUDY DRUG

7.1. Study Drug Description

A large black rectangular redaction box covering the content of the Study Drug Description section.

[figure not shown]
7.2. Packaging and Labeling

[figure not shown]
The Sponsor will provide the Investigator with packaged ISIS 766720 labeled in accordance with specific country regulatory requirements.

7.3. Study Drug Accountability

The study staff is required to document the receipt, dispensing, and return/destruction of ISIS 766720 supplies provided by the Sponsor according to Sponsor instruction and in accordance with institutional policy.

8. TREATMENT OF PATIENTS

A large black rectangular redaction box covering the content of the Treatment of Patients section.

8.2. Other Protocol-Required Drugs

There are no other protocol related drugs for this study.

8.3. Other Protocol-Required Treatment Procedures

There are no other protocol required treatment procedures.

8.4. Treatment Precautions

There are no specific treatment precautions required for this study.

8.5. Safety Monitoring Rules

Please refer also to the 'Guidance for Investigator' section of the Investigator's Brochure.

For the purposes of safety monitoring Baseline is defined as:

- Monitoring Rules for Liver Chemistry Tests, Renal parameters, and Platelets – Unless otherwise specified, baseline is defined as the average of pre-dose values

In addition to the standard monitoring of clinical safety parameters, the following guidelines are provided for the monitoring of selected parameters chosen based on preclinical and clinical observations for ISIS 766720 as well as other ASOs.

Confirmation Guidance: At any time during the study (Treatment or Post-Treatment Periods), the initial clinical laboratory results meeting the safety monitoring criteria presented below **must be confirmed** by performing measurements (ideally in the same laboratory that performed the initial measurement) on new specimens. All new specimen collections should take place as soon as possible (ideally within 7 days of the initial collection). For stopping rules, if the initial laboratory result is observed during the Treatment Period, the results from the re-test **must be available** prior to administering the next dose of ISIS 766720.

Re-dosing Guidance: Patients with initial laboratory test values that reach a stopping rule must not be re-dosed until the re-test results are available. In general, patients who do not meet the

stopping rules based upon re-test may continue dosing. However, the Investigator and the Sponsor Medical Monitor (or appropriately qualified Designee) should confer as to whether additional close monitoring of the patient is appropriate. If any of the stopping criteria described in Section 8.6 are met, the patient will be permanently discontinued from further treatment with ISIS 766720, evaluated fully as outlined below and in consultation with the Sponsor Medical Monitor (or appropriately qualified Designee), and will be followed up in accordance with Section 8.8 of the Protocol.

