8.5.2. Safety Monitoring Rules for Platelet Count Results

An evaluable platelet count is required prior to each dose during the Treatment Period. Treatment should be held if there is no evaluable platelet count within the 2 weeks (+7 days) up to Week 17 and within 4 weeks (+7 days) after Week 17 prior to the scheduled dose. Any unreportable platelet count result must be rechecked and determined not to have met a stopping rule before dosing can continue. Central laboratory is preferred; however, a local laboratory may be utilized to ensure a platelet value is available prior to dosing.

If a patient's absolute platelet count is $\geq 75,000/\text{mm}^3$ to $\leq 100,000/\text{mm}^3$, then the patient's platelet counts should be monitored weekly. In case of platelet count below $75,000/\text{mm}^3$, the platelet monitoring rule defined in Stopping Rules (Section [8.6.3](#)) should be followed.

In the event of a platelet count $< 75,000/\text{mm}^3$, additional laboratory investigations may be conducted in consultation with Sponsor Medical Monitor or Designee.

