8.6.1. Stopping Rules for Liver Chemistry Elevations

In the event of laboratory results meeting the following criteria, **and the event is without an alternative explanation as discussed with the Sponsor Medical Monitor** (or appropriately qualified Designee), dosing of a patient with ISIS 766720 will be stopped permanently; values that are not confirmed due to failure to retest or missing lab values will be presumed confirmed:

1. ALT or AST $> 8 \times$ ULN, which is confirmed
2. ALT or AST $> 5 \times$ ULN, which is confirmed and persists for ≥ 2 weeks
3. ALT or AST $> 3 \times$ ULN or the greater of $2 \times$ baseline value or $3 \times$ ULN if the baseline value was $>$ ULN, which is confirmed **and** total bilirubin $> 2 \times$ ULN or INR > 1.5
4. ALT or AST $> 3 \times$ ULN or the greater of $2 \times$ baseline value or $3 \times$ ULN if the baseline value was $>$ ULN with the new appearance (i.e., onset coincides with the changes in hepatic enzymes) of fatigue, nausea, vomiting, right upper quadrant pain or tenderness, fever, rash, and/or concomitant eosinophilia ($>$ ULN)

8.6.2. Stopping Rules for Renal Function Test Results / Temporary Stopping Rules for Renal Function Test Results

In the event of a persistent elevation that is observed over 2 consecutive weeks, for either of the 2 criteria below, dosing of a patient with ISIS 766720 will be suspended temporarily:

1. Serum creatinine increase that fulfills all of the following: ≥ 0.3 mg/dL (26.5 μ mol/L) **and** $\geq 40\%$ above baseline creatinine values **and** $>$ ULN (refer to definition of baseline in Section 8.6)
2. Proteinuria, UPCR > 750 mg/g for baseline > 200 mg/g, or $4 \times$ baseline for baseline < 200 mg/g that is confirmed by repeated UPCR or by a quantitative total urine protein measurement of > 1.0 g/24 hour

The possible dosing re-initiation or follow-up schedule for any events meeting either of these criteria will be determined by the Investigator **in consultation with** the Sponsor Medical Monitor or Designee.

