8.6.3. Stopping Rule for Platelet Count Results

In the event of any platelet count less than $50,000/\text{mm}^3$, dosing of the patient with ISIS 766720 will be stopped permanently. Platelet count will be monitored at least twice weekly until 3 successive values $> 75,000/\text{mm}^3$ then weekly until 3 values $> 100,000/\text{mm}^3$ ([Table 4](#)).

Administration of steroids is recommended for patients whose platelet count is less than $25,000/\text{mm}^3$. Treatment guidelines for immune thrombocytopenia ([Provan et al. 2010](#)) recommend Dexamethasone 40 mg daily for 4 days every 2-4 weeks for 1-4 cycles; Prednis(ol)one 0.5-2 mg/kg/d for 2-4 weeks then taper; or methylprednisolone 30 mg/kg/day for 7 days.

Note: Patient may require continuation with oral steroids after methylprednisolone treatment is stopped.

In the event of a platelet count $< 75,000/\text{mm}^3$ and $> 50,000/\text{mm}^3$, and in the absence of MB or clinically relevant non-major bleeding (CRNMB) (defined below; ([Schulman and Kearon 2005](#); [Buller et al. 2007](#)) , dosing with ISIS 766720 should be suspended temporarily until the platelet count has recovered to $> 100,000/\text{mm}^3$. The suitability of the patient for continued dosing will be determined by the Investigator in consultation with the Sponsor Medical Monitor or Designee and will be based on factors such as the original rate of decline in the patient's platelet count, whether any bleeding events were experienced, and the speed of recovery of platelet count after interruption of dosing. If dosing is reinitiated, platelet count must be measured weekly until the end-of-study.

If, after reintroduction of ISIS 766720, the platelet count falls below $75,000/\text{mm}^3$, further dosing of the patient with ISIS 766720 will be stopped permanently.

Definition of Major Bleeding Events ([Schulman and Kearon 2005](#)):

1. Fatal bleeding, and/or
2. Symptomatic bleeding in a critical area or organ, such as intracranial, intraspinal, intraocular, retroperitoneal, intraarterial or pericardial, or intramuscular with compartment syndrome
3. Clinically overt bleeding leading to transfusion of ≥ 2 units of packed red blood cells or whole blood or a fall in hemoglobin of 2.0 mg/dL (1.24 mmol/L) or more within 24 hours

Definition of Clinically Relevant Non-Major Bleeding Events ([Buller et al. 2007](#)):

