Clinically relevant CRNMB is defined as overt bleeding not meeting the criteria for MB but that resulted, for example, in medical examination, intervention, or had clinical consequences for a patient.

Definition of Minor Bleeding Events:

Minor bleeding events are those that do not fulfill the criteria for MB or CRNMB (defined above).

Table 4: Actions in Patients with Low Platelet Count

Platelet Count	Drug Dose	Monitoring
> 100,000/mm ³	No action	Monitor per Schedule of Procedures every 2 weeks (+7 days) up to Week 17 and every 4 weeks (+7 days) after Week 17
≥ 75,000 to ≤ 100,000/mm ³	No action	Monitor every week until 3 successive values > 100,000/mm ³
≥ 50,000 to < 75,000/mm ³	Pause dosing When platelet count returns to > 100,000/mm ³ restart dosing only if approved by Sponsor Medical Monitor or Designee	Monitor at least twice weekly until 3 successive values > 75,000/mm ³ then weekly until 3 values > 100,000/mm ³ . If redosing then continue to monitor weekly for the remainder of the Treatment Period. If not redosing then subsequent monitoring should be per the Schedule of Procedures. Consider discontinuation of antiplatelet agents/non-steroidal anti-inflammatory drug (NSAIDS)/anticoagulant medication while platelet count < 75,000/mm ³ .
≥ 25,000 to < 50,000/mm ³	Permanently discontinue ISIS 766720	Monitor twice weekly until 3 successive values > 75,000/mm ³ then weekly until 3 values > 100,000/mm ³ . Subsequent monitoring should be per the Schedule of Procedures. Discontinue antiplatelet agents/NSAIDS/anticoagulant medication while platelet count < 75,000/mm ³ if possible.
< 25,000/mm ³	Permanently discontinue ISIS 766720	Monitor daily until 3 successive values show improvement then monitor twice weekly until 3 successive values > 75,000/mm ³ then weekly until 3 values > 100,000/mm ³ . Subsequent monitoring should be per the Schedule of Procedures. Steroids recommended* Consider need for hospitalization and referral to hematologist Discontinue antiplatelet agents/ NSAIDS/ anticoagulant medication while platelet count < 75,000/mm ³ if possible

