8.8. Discontinuation of Study Drug/Treatment

A patient must permanently discontinue study treatment for any of the following:

- The patient becomes pregnant. Report the pregnancy according to instructions in Section [9.4](#)
- The patient withdraws consent
- The patient experiences an AE that necessitates permanent discontinuation of ISIS 766720
- The patient develops laboratory test abnormalities that meet any of the stopping rules listed in Sections [8.6.1](#) to [8.6.3](#)
- The patient meets any of the following Exclusion Criteria (see Section [5.2](#)) after discussion with the Sponsor Medical Monitor (or appropriately qualified Designee)
 - Patient needing pituitary surgery or radiation during Treatment Period
 - Patient with a pituitary tumor that is worsening (e.g., either growing, or at risk of compressing or abutting the optic chiasm or other vital structures) as assessed by pituitary/sellar MRI protocol
 - Treatment with any other acromegaly medications

The reason for discontinuation of ISIS 766720 must be recorded in the electronic Case Report Form (eCRF) and source documentation.

Patients who discontinue ISIS 766720 should complete early termination from treatment visit (ETTX) and then enter the Post-Treatment Period) unless consent is withdrawn. Minimally, every effort should be made to complete the ETTX (see [Appendix A](#), Section [6.1.2](#)).

If the patient declines or is unable to participate in the above, the Investigator should clarify what type of follow-up the patient is agreeable to: in person, by phone/mail, through family/friends, via correspondence/communication with other physicians, and/or from review of the medical records. Wherever possible, these patients should continue to be followed up via the agreed means to collect information on AEs, concomitant medications and survival status. At the very least, the patient's status at the end of the protocol defined study period should be ascertained and documented wherever possible. The agreed means of follow-up will be documented in the patient records and the Sponsor notified.

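### Protocol 8.5 and 8.8 require permanent discontinuation for any Section 8.6 stopping rule, but 8.6.2 only suspends dosing for both renal criteria; one platelet band in 8.6.3 probably conflicts too

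*Combined protocol and SAP*

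**What the plan says.** **General rules.** The re-dosing guidance in Protocol 8.5 reads: "If any of the stopping criteria described in Section 8.6 are met, the patient will be permanently discontinued from further treatment with ISIS 766720". Protocol 8.8 opens its list with "A patient must permanently discontinue study treatment for any of the following", and one item is: "The patient develops laboratory test abnormalities that meet any of the stopping rules listed in Sections". The range that this item then gives runs from 8.6.1 to 8.6.3 and so includes 8.6.2. Neither section makes an exception.

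**Renal rules.** Section 8.6.2, whose heading uses both the stopping-rule label and a temporary-stopping-rule label, has two criteria: a persistent serum creatinine rise and persistent proteinuria measured by UPCR. For either one, "dosing of a patient with ISIS 766720 will be suspended temporarily". On what follows, it says: "The possible dosing re-initiation or follow-up schedule for any events meeting either of these criteria will be determined by the Investigator". The sponsor's medical monitor, or a designee, has to be consulted on that decision.

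**Platelet rules.** For a count between 50,000 and 75,000/mm³ without major or clinically relevant non-major bleeding, 8.6.3 says "dosing with ISIS 766720 should be suspended temporarily until the platelet count has recovered". For the corresponding band, Table 4 pauses dosing and says "restart dosing only if approved by Sponsor Medical Monitor or Designee". Section 8.5.2 sends counts below 75,000/mm³ to "the platelet monitoring rule defined in Stopping Rules", citing 8.6.3. Counts below 50,000/mm³, and a fall below 75,000/mm³ after reintroduction, are permanent stops.

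**The concern.** For a persistent renal abnormality the protocol gives two instructions that cannot both be carried out. Restarting under 8.6.2 breaches the obligation in 8.8. Following 8.8 moves the patient to the early termination visit (ETTX) and the Post-Treatment Period, and the restart provision in 8.6.2 then has no use.

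The main stake is a mandatory safety rule that sites can read in two ways. There are also consequences for the data:

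- The SAP (3.7.2) tabulates treatment-emergent adverse events leading to permanent discontinuation. Where the abnormality is recorded as an adverse event, the reading used can decide whether it appears there, at any time in the study.
- For events before Week 27 only, the reading can affect membership of the PPS, which is the basis of the primary efficacy analysis (Protocol 10.6), and whether a Week 27 IGF-1 value exists.

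**Working it through.** **1. Each provision in 8.6 against 8.5 and 8.8**

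| Provision | Action in 8.6 | Action in 8.5 and 8.8 | Agree? |
|---|---|---|---|
| 8.6.1, liver criteria 1 to 4 | Permanent stop | Permanent stop | Yes (4) |
| 8.6.2, creatinine | Temporary suspension, restart possible | Permanent stop | No |
| 8.6.2, UPCR | Temporary suspension, restart possible | Permanent stop | No |
| 8.6.3, platelets <50,000/mm³ | Permanent stop | Permanent stop | Yes |
| 8.6.3 and Table 4, first fall to about 50,000 to <75,000/mm³ | Pause, restart possible | Permanent stop, if this counts as a stopping rule | Probably not |
| 8.6.3, <75,000/mm³ after reintroduction | Permanent stop | Permanent stop | Yes |

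Total: 4 + 2 + 3 = 9 provisions. Two conflict clearly, one probably, and six agree. The nine is a count made for this review; the protocol gives no such figure.

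**2. Inside the platelet band**

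The 8.6.3 text covers counts above 50,000/mm³ without major or clinically relevant non-major bleeding. Table 4 covers counts of 50,000/mm³ or more and sets no bleeding condition. A count of exactly 50,000/mm³, or a count in the band with such bleeding, therefore has an action in Table 4 but none in the 8.6.3 text.

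**3. Dose count for the PPS**

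Inputs:

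- The PPS needs at least 6 of the 8 doses in the first 27 weeks (Protocol 10.3).
- Doses are monthly with a Day 15 booster (3.4).
- The PK schedule (Appendix C) has a pre-dose sample at Week 25 and an any-time sample at Week 27, so no dose is due at Week 27.

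This gives doses at Weeks 1, 3, 5, 9, 13, 17, 21 and 25, which are Days 1, 15, 29, 57, 85, 113, 141 and 169. That is 8 doses. Continuing every 4 weeks from Week 29 to Week 73 adds 12, and 8 + 12 = 20 matches the maximum in 6.1.2.

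The fifth dose is on Day 85 (Week 13) and the sixth on Day 113 (Week 17). At most 8 − 6 = 2 doses can be missed.

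- **Last dose before the event at Week 13 or earlier.** A permanent stop gives at most 5 of 8, which fails. A hold missing 1 dose gives 7 and a hold missing 2 gives 6, and both pass. A hold missing 3 or more gives at most 5 and fails under either reading.
- **Last dose at Week 17 or 21.** The patient already has 6 or 7 doses, so the count is met either way.

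**4. The Week 27 value (Day 183)**

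For a last dose at Week 17, Day 183 is 183 − 113 = 70 days later. For Week 21 it is 183 − 141 = 42 days later. After a permanent stop, ETTX and the Post-Treatment visits replace the Week 27 visit. The SAP summarises by visit label (3.2.1) and does not impute missing IGF-1 (3.3.5).

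Under a hold the Week 27 visit stays on the schedule. SAP 3.2.1, however, leaves out of the by-visit summaries any PD result more than 21 days after the last dose and up to treatment termination. Both 70 and 42 exceed 21. If a hold is never lifted, the Week 27 value drops out of those summaries as well. For these patients the readings differ on this point only if dosing later resumes.

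For a last dose at Week 25, all 8 doses have been given and Day 183 is 183 − 169 = 14 days later, inside the 21-day limit. ETTX is preferably 4 weeks after the last dose, Day 169 + 28 = 197. Whether a Week 27 assessment is still made then depends on when the stop is decided.

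**The case against.** The strongest reply is that the specific text governs the general one. Section 8.5.4 sends a persistent renal elevation straight to 8.6.2, whose heading says the rule is temporary. Section 8.7 allows interruptions for safety, and 9.4.3.3 has a category for interrupted and restarted dosing. On this view the defect is an over-broad cross-reference in 8.8, and a site that suspends dosing and never restarts breaches neither text.

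The cross-reference may well be the origin of the problem. But none of these sections limits 8.8 or says which text prevails, and the 8.6.2 heading also carries the stopping-rule label that 8.8 uses. A hold that is never lifted still differs from 8.8, which sends the patient to ETTX and the Post-Treatment Period.

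Several other points stand in whole or part:

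- Dosing halts under both readings, and restart involves the Sponsor Medical Monitor (consultation in 8.6.2 and 8.6.3, approval in Table 4). This limits inconsistent handling. It does not remove it, because 8.8 leaves no restart to consider.
- The platelet conflict is less firm. The 8.6.3 title is singular and its opening rule is permanent, while 8.5.2 describes the provision for counts below 75,000/mm³ as a monitoring rule, although one located in the stopping rules. It is graded probable and carries no weight in the severity.
- The Week 27 consequences are conditional, as the working shows, and do not carry the severity either.

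**Conclusion.** The concern holds and must be fixed. For both renal criteria, 8.5 and 8.8 require permanent discontinuation, while 8.6.2 prescribes a temporary suspension with possible restart, and nothing in the available text reconciles them. The severity rests on this renal conflict alone. The platelet band is a probable third conflict, with a separate mismatch between 8.6.3 and Table 4. The liver rules, counts below 50,000/mm³ and a fall below 75,000/mm³ after reintroduction are consistent with 8.5 and 8.8.

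The effect on the primary analysis is limited to events before Week 27. It can change PPS membership when the last dose before the event is at Week 13 or earlier and a hold would miss no more than 2 of the 8 doses. For a last dose at Week 17 or 21 it can change whether a Week 27 value is available for the by-visit summaries, provided dosing would have resumed under a hold. Later events do not touch the primary endpoint. The dose days assume the nominal schedule, and the size of the effect cannot be estimated because event frequency is not given.

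**What to change.** Reconcile 8.5 and 8.8 with 8.6.2, 8.6.3 and Table 4 so that:

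- each laboratory criterion has one stated action;
- the cross-references in 8.5 and 8.8 name only the criteria to which permanent discontinuation applies;
- the platelet band limits and the bleeding condition are the same in 8.6.3 and Table 4.

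Which action applies to each criterion is a decision for the sponsor's medical team, and this review takes no position on it.

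The cost is wording in the next protocol amendment and a letter to sites. No new procedures or patients are needed.
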